The effect of high intensity interval vs moderate continuous endurance exercise training on program adherence

Introduction & Background

For optimal health, current Canadian physical activity guidelines recommend 150 minutes of moderate intensity or 75 minutes of vigorous-intensity endurance exercise training per week. Yet many Canadians fail to meet these recommendations apparently due to lack of time. Recently, several studies observed that very brief, repeated exercise bouts at high intensity promote similar health and exercise performance benefits as those found with moderate endurance training of much longer duration. For example, MacPherson and colleagues (2011) has compared brief, sprint vs much longer continuous endurance exercise training and found similar improvements for endurance capacity and exercise performance. Similarly, Gillen et al. (2014) found three 20 second bouts of high interval training at an all-out effort intensity elicited similar physiological benefits as to 50 minutes of moderate endurance training. Further, another recent study found short, repeated bursts of high-intensity training over 12 weeks had similar health benefits as 50 minutes of moderate endurance training (Gillen et al., 2016). The current study will follow a similar exercise training protocol as Gillen et al. (2016) however, importantly, will control exercise time (20 minutes in both groups) because it is assumed that the shorter duration in the high intensity groups of previous studies may contribute to greater program adherence rates.

Research Objectives

1. To determine whether high-intensity interval training (HIIT) group experience a greater program adherence than moderate continuous endurance exercise training (MCEET) group when matched for time commitment of 20 minutes
2. To assess whether HIIT group results in greater improvements in fat loss and endurance capacity than MCEET group

Research Hypothesis

The study hypothesizes that HIIT group will result in greater program adherence than MCEET. Also, HIIT group will result in greater improvements in fat loss and endurance capacity vs. MCEET group.

Methods

40 healthy adults aged 19 to 35 years (20 men, 20 women) will participate in the study. Participants will be recruited from Western University and its surrounding community via university poster. Interested participants will be asked to come to the Exercise Nutrition Research Laboratory ([name]) for a face-to-face interview with the investigator and to complete Get Active Questionnaire (GAQ) that includes medical history for pre-screening eligibility. Inclusion criteria include healthy participants between the ages of 19 to 35 years who engage in physical activity less than three times per week. They must be able to run a mile, have an access to the gym as well as smart phones (such as Android, Cat phone, Google Nexus, Samsung Galaxy, iPhone, Microsoft Lumia, myTouch or Phablets) and can access to Apps (such as MyFitnessPal, Rise Up, Calorific, My Diet Coach, Yazio, On The Regimen, See How You Eat, Lost It, MyNetDiary or MyPlate). Exclusion criteria include diabetic, pregnant, individuals with a history of fainting, low and high blood pressure, heart disease, respiratory disease, migraines, heartburn, smokers, engage in physical activity

more than two times per week and answering YES to any questions from page 1 of GAQ. Eligible participants will be provided with the written informed consent.

Once completed, all participants will complete body composition testing via air displacement plethysmography (Bod Pod) pre and post intervention (week 0 and 6). Following Bod Pod measurements, participants will run a practice mile run for familiarity and will run again for measurement purposes before and after the exercise intervention to assess their endurance capacity. Time will be measured by a stopwatch. Participants will be match-paired based on their endurance capacity to either HIIT or MCEET group for five weeks. They will fill out two validated questionnaires, physical activity enjoyment scale (PACES) and exercise adherence rating scale (EARS) after the 6th, 9th and 15th session to assess their program adherence. They will be instructed not to engage in any either exercise program during the study period.

The first week of the exercise intervention will consist of one-on-one supervised treadmill training, three times per week in the lab. From week two to five, participants will follow the same exercise program on their own at their preferred gym three times per week in order to examine free-living individuals adhere to two exercise programs. Each participant will be matched to either HIIT or MCEET group based on their timed one-mile run. The HIIT group will perform six, 20-second bouts of high intensity interval exercise separated by 2 minutes of active recovery (walking) while the MCEET group will perform 14 minutes of continuous endurance exercise at 70% Maximum Heart Rate (MHR). Both exercise protocols will include 3 minutes of warm up and cool down at a 30% MHR, for a total of 20 minutes for each treatment.

Ratings of perceived exertion (RPE; Borg CR-10 scale) will be recorded at the end of each interval for HIIT group and at 10 and 20 minutes of exercise for MCEET group on the 6th, 9th and 15th session. All participants will log their heart rate before, during, and immediately after each training session using Fitbit or a free heart rate monitor mobile App (e.g. Argos) to ensure safety and achievement of their targeted heart rate. Participants will also complete physical activity enjoyment scale (PACES) and exercise adherence rating scale (EARS) on the 6th, 9th and 15th session to assess their program adherence. To accommodate progression, training intensity will be adjusted to maintain the desired relative exercise intensity based on above measurements. Finally, no attempt will be made to modify the participants daily diet, but a 3-day food log will be collected via free mobile app (e.g. MyFitnessPal) to assess food intake for any change. Completed questionnaires and the recorded heart rate data saved on Fitbit or a mobile app will be used to confirm program adherence.

All the collected data will be statistically analyzed by Sigma Plot 12.0 (Systat Software, San Jose, CA, USA) using a two-way analysis of variance (ANOVA), Tukey's post hoc test, and a paired t-test. Significance set at $p < 0.05$. Sample size estimates are generated with a two-way analysis of variance (ANOVA). The primary outcome variable is the program adherence, with a minimum important difference of 19.6 between HIIT (103.8 ± 9.4) and MCEET (84.2 ± 19.1 ; Thum, Parsons, Whittle & Astorino, 2017). Based on the data from Kadam & Bhalerao (2010), we calculate the pooled variance (19.1), effect size f (0.8), and Cohen's d (1.96) for the sample size estimation.

Using ANOVA, match-paired study design, a minimum of 15 participants is required for an alpha of 0.05 and 95% power. 34% of drop out rate (Linke, Gallo & Norman, 2011) will be included in addition to the minimal sample size resulting in 20 participants for each group.

References

- Gillen, J. B., Martin, B. J., MacInnis, M. J., Skelly, L. E., Tarnopolsky, M. A., & Gibala, M. J. (2016). Twelve weeks of sprint interval training improves indices of cardiometabolic health similar to traditional endurance training despite a five-fold lower exercise volume and time commitment. *PloS one*, *11*(4), e0154075.
- Gillen, J. B., Percival, M. E., Skelly, L. E., Martin, B. J., Tan, R. B., Tarnopolsky, M. A., & Gibala, M. J. (2014). Three minutes of all-out intermittent exercise per week increases skeletal muscle oxidative capacity and improves cardiometabolic health. *PLoS One*, *9*(11), e111489.
- Kadam, P., & Bhalerao, S. (2010). Sample size calculation. *International Journal of Ayurveda Research*, *1*(1), 55–57. <http://doi.org/10.4103/0974-7788.59946>
- Linke, S. E., Gallo, L. C., & Norman, G. J. (2011). Attrition and adherence rates of sustained vs. intermittent exercise interventions. *Annals of Behavioral Medicine*, *42*(2), 197.
- Macpherson, R. E., Hazell, T. J., Olver, T. D., Paterson, D. H., & Lemon, P. W. (2011). Run sprint interval training improves aerobic performance but not maximal cardiac output. *Medicine & Science in Sports & Exercise*, *43*(1), 115-122.
- Thum, J. S., Parsons, G., Whittle, T., & Astorino, T. A. (2017). High-Intensity Interval Training Elicits Higher Enjoyment than Moderate Intensity Continuous Exercise. *PloS one*, *12*(1), e0166299.

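### The plan recruits equal numbers of men and women but neither pairs by sex nor specifies a sex factor, so a chance sex imbalance between arms can arise and go unadjusted

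*Combined protocol and SAP*

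**What the plan says.** The combined protocol and SAP mentions sex once in its design and analysis text, in the opening sentence of Methods: "40 healthy adults aged 19 to 35 years (20 men, 20 women) will participate in the study".

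Allocation is described twice in Methods, each time on one variable. The recruitment and testing text says "Participants will be match-paired based on their endurance capacity to either HIIT or MCEET group for five weeks". The exercise-intervention text says "Each participant will be matched to either HIIT or MCEET group based on their timed one-mile run". Neither names sex as a pairing or stratifying variable, and neither says that assignment within a pair is random.

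The statistical paragraph at the end of Methods says the data will be analysed "using a two-way analysis of variance (ANOVA), Tukey's post hoc test, and a paired t-test". It does not name the two ANOVA factors and mentions no covariate.

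The outcomes most affected are those of the second research objective: "To assess whether HIIT group results in greater improvements in fat loss and endurance capacity than MCEET group". They are secondary: "The primary outcome variable is the program adherence".

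**The concern.** Fixing the sample at half men and half women suggests that the sponsor regards sex as important. A quota on the whole sample does nothing for the comparison between arms, which depends on how the 20 men are divided between HIIT and MCEET. Pairs formed on mile time alone may contain one man and one woman, and every such pair can tilt the sex mix of the arms.

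If men and women respond differently in fat loss or mile time, an uneven split adds avoidable error to a comparison of 20 with 20, or of about 13 with 13 after the planned dropout (20 × 0.66 = 13.2). With no sex factor specified, nothing in the written analysis would remove that error.

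**Working it through.** **Inputs from the documents.** 40 participants, 20 men and 20 women; 20 per arm; 34% dropout (all from Methods). The plan gives no figure for sex balance to reproduce. The arm size itself does reproduce: 15 × 1.34 = 20.1, hence 20 per group and 40 in total.

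**Assumed inputs.** The documents do not give the sex gap in mile time, the sex difference in change, or the share of residual variance due to sex. Each is varied below. Random assignment within pairs is also assumed.

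**1. Upper end: sex unrelated to mile time.** The number of men X in one arm is hypergeometric, P(X = x) = C(20, x) × C(20, 20 − x) / C(40, 20).

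- C(20,10)² = 184,756² = 34,134,779,536; C(20,9)² = 167,960² = 28,210,561,600; C(40,20) = 137,846,528,820.
- P(9 ≤ X ≤ 11) = (34,134,779,536 + 2 × 28,210,561,600) / 137,846,528,820 = 0.657.
- P(12:8 or worse) = 1 − 0.657 = 0.343.
- Adding 2 × C(20,8)² = 2 × 125,970² to the numerator gives P(8 ≤ X ≤ 12) = 0.887, so P(13:7 or worse) = 0.113.

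**2. The allocation described: pairing on mile time.** Simulation: rank 40 people on mile time, pair neighbours, and assign each pair by coin flip.

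| Assumed sex gap in mile time | Mean mixed-sex pairs of 20 | 12:8 or worse | 13:7 or worse |
|---|---|---|---|
| none | 10 | 34% | 11% |
| 1 SD | 8 | 28% | 7% |
| 2 SD | 5 | 15% | 2% |
| 3 SD | 2 | 2.5% | about 0% |

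**3. Effect of an imbalance.** The shift in an unadjusted arm difference is the difference in the proportion of men times the sex difference in the outcome. For 12:8 the multiplier is 12/20 − 8/20 = 0.2; for 13:7 it is 13/20 − 7/20 = 0.3. With an assumed sex difference in change of 0.25, 0.5 or 1 SD, a 12:8 split shifts the comparison by 0.05, 0.10 or 0.20 SD, and a 13:7 split by 0.075, 0.15 or 0.30 SD.

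**4. Pairing within sex.** 20 men form 10 pairs and 20 women form 10 pairs, so each arm starts with 10 of each. The chance of imbalance at allocation is zero.

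**5. After dropout.** With 10 men and 10 women per arm and independent 34% dropout at the same rate in all groups, simulation gives about a 10% chance that the proportion of men among completers differs between arms by 20 percentage points or more.

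**6. Precision from adjusting for sex.** In a between-group model of change, the ratio of standard errors with and without sex is √[(1 − R²) × 38/37] for 40 people, where R² is the share of residual variance that sex explains.

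- R² = 0.10: √(0.90 × 1.027) = 0.961, a cut of about 4%.
- R² = 0.30: √(0.70 × 1.027) = 0.848, a cut of about 15%.

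**The case against.** Several stronger readings are tempting, and the documents do not support them.

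- **That the analysis has no sex term.** The ANOVA factors are unnamed, so group by sex is not excluded. Group by time is the likelier reading for pre/post data, but all that can be said is that no sex factor is specified.
- **That the risk of a 12:8 split is simply 34%.** That figure belongs to allocation unrelated to sex. It is the upper end of the range and falls as the sex gap in mile time grows.
- **That the comparison would be biased.** Chance imbalance under random assignment is imprecision. Since random assignment within pairs is not stated, the probabilities above are themselves conditional on it.
- **That sex differences in body fat or mile time are enough to distort the result.** The second objective concerns improvement from baseline. A difference in level cancels in a change score; only a sex difference in change matters, and the documents do not quantify one.
- **That endurance and fat loss are equally exposed.** Mile-time pairing balances baseline endurance directly, and sex indirectly so far as sex tracks mile time. Nothing in the allocation is matched on body composition.

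It can also be said that matching on the one variable tied to a study outcome is a legitimate choice in a 40-person study, that only secondary outcomes are at stake, and that adding a sex main effect may achieve nothing. The last point has force. A sex main effect does not sharpen a group-by-time test, and sex drops out of a paired analysis when pairs are formed within sex. The model change must therefore be specified with care. None of this removes the case for pairing within sex, which keeps the mile-time matching and needs no extra participants.

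**Conclusion.** The point holds in a limited form. The plan has a sex quota, no device for balancing sex between arms, and no specified sex factor. The chance of 12:8 or worse runs from 34% down to about 2.5% across assumed sex gaps in mile time of 0 to 3 SD, given random assignment within pairs. The consequence is a shift of 0.2 times any sex difference in change: 0.05 to 0.20 SD for assumed differences of 0.25 to 1 SD. It falls mainly on fat loss. Nothing in the documents shows that sex affects adherence, so the point does not extend to the primary outcome. It is a low-severity improvement.

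**What to change.** **Allocation.** Form 10 pairs of men and 10 pairs of women, each matched on mile time, so that each arm starts with 10 men and 10 women. State whether assignment within pairs is random.

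**Analysis.** Name the two ANOVA factors. Because dropout can break pairs and disturb the sex balance, include sex in the between-group models of change for fat and mile time. If a repeated-measures ANOVA is used instead, include sex by time, since a sex main effect alone would not help the group-by-time test.

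**Cost.** A sentence on allocation and a line on the model. The downsides are slightly looser mile-time matches and one degree of freedom. In return, sex is balanced exactly at allocation, and the standard error of the between-group difference in change would fall by about 4% to 15% if sex explains the assumed 10% to 30% of residual variance.

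### The questionnaires that assess adherence, the primary outcome, are tied to session number, with no stated way to obtain scores from people who stop or skip sessions

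*Combined protocol and SAP*

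**What the plan says.** The document is a combined protocol and SAP; everything on this point is in its Methods.

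- **Primary outcome** (statistical paragraph): "The primary outcome variable is the program adherence". No single instrument or time point is named as primary.
- **Questionnaires** (paragraph on baseline testing and matching): PACES and EARS are completed "after the 6th, 9th and 15th session to assess their program adherence". The later paragraph on RPE and heart rate recording repeats the schedule as "on the 6th, 9th and 15th session to assess their program adherence".
- **Supervision** (training paragraph): week 1 is supervised in the laboratory. After that, "From week two to five, participants will follow the same exercise program on their own".
- **Heart rate logs**: participants log heart rate at each session, and together with the completed questionnaires "the recorded heart rate data saved on Fitbit or a mobile app will be used to confirm program adherence".
- **Analysis**: "All the collected data will be statistically analyzed by Sigma Plot 12.0", with ANOVA, Tukey's test and a paired t-test. No missing-data method is given.
- **Dropout**: 34% is expected, and the allowance "will be included in addition to the minimal sample size resulting in 20 participants for each group".

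The Methods give no calendar date or window for the questionnaires, no follow-up of people who stop, and no rule for a questionnaire that is never reached. Body composition is measured at weeks 0 and 6, but the week-6 visit is not named as an occasion for collecting questionnaires.

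**The concern.** In most exercise trials dropout is a nuisance. Here it is close to the outcome itself. If the 15th session means the 15th session done, a participant must keep training to be asked about adherence, and the least adherent are the least measured. Scores at the 9th and 15th sessions would then come mainly from people still training, and the comparison would drift from the groups as allocated towards those who stayed. Recruiting more people yields more scores but leaves that selection in place.

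The heart rate logs could show who did how many sessions. The plan mentions them only as confirmation, so the most direct record of adherence has no defined summary and no defined comparison between groups.

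**Working it through.** **1. Where the questionnaires fall.** Three sessions a week for five weeks is 3 × 5 = 15 sessions. Week 1 (sessions 1 to 3) is supervised, so 15 − 3 = 12 sessions (4 to 15) are unsupervised. Sessions 6, 9 and 15 are the last scheduled sessions of weeks 2, 3 and 5.

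**2. The two readings.**

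| Participant | Session number = sessions done | Session number = scheduled date |
|---|---|---|
| Stops after session 3 | 0 of 3 scores | Three dates; no stated way to reach them |
| Stops after session 7 | 1 of 3 scores | Two dates left; no stated way to reach them |
| Skips sessions, stays enrolled | Never reaches session 15 unless sessions are made up, which the plan does not mention | Could be asked on the date |

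Selection on attendance is built into the first reading only. The missing follow-up and missing-score rule apply to both.

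**3. Scale of the loss.** The plan's dropout step reproduces as 15 × 1.34 = 20.1, about 20 per group, which is why its minimum of 15 is read here as per group. At 34% dropout, 20 × 0.34 = 6.8 per arm could lack a session-15 score.

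**4. What that loss could do to the difference.** Inputs from the statistical paragraph: means 103.8 and 84.2 (difference 19.6), SDs 9.4 and 19.1. Pooled SD = √((9.4² + 19.1²)/2) = 15.05.

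Assumptions not in the documents: scores are normal; the log-odds of still being measured at session 15 rise by 0.5, 1 or 2 per 15.05 points of score; and loss splits between arms as shown. The last null row uses a true difference of 0.

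| Loss pattern at session 15 | Difference seen, plan SDs (slopes 0.5 / 1 / 2) | Difference seen, both SDs 15.05 |
|---|---|---|
| 34% in each arm | 16.8 / 15.1 / 14.0 | 19.6 / 19.6 / 19.6 |
| Loss follows score alone, 34% overall | 15.8 / 12.0 / 7.4 | 18.6 / 16.8 / 13.7 |
| HIIT 47%, MCEET 21% | 18.6 / 18.0 / 18.1 | 21.4 / 22.7 / 24.1 |
| HIIT 21%, MCEET 47% | 15.0 / 12.1 / 9.8 | 17.8 / 16.5 / 15.1 |
| No true difference, 47% in one arm and 21% in the other | not run | 1.8 / 3.1 / 4.5, favouring the arm that loses more |

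If score and staying on are unrelated (slope 0), every row with a true difference returns 19.6. With equal loss, the shrinkage in the plan-SD column comes only from the unequal SDs. Across the rows with a true 19.6, the observed value runs from 7.4 to 24.1. The table shows that bias is possible in either direction; it predicts neither direction nor size.

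**The case against.** **The session numbers may only be labels for the ends of weeks 2, 3 and 5.** In a fixed three-a-week program that is a natural reading, and the documents do not exclude it. It stands. On that reading selection is not built into the timing; what remains is the absence of follow-up for people who stop and of a missing-score rule.

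**The bias figures rest on assumptions.** True: no slope or arm split comes from the documents. The plan also does not say whether the means and SDs belong to PACES or EARS, and the study cited for them concerns enjoyment. A reader might infer that the trial is biased against one arm, or by a given amount. The documents do not support that.

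**The shortfall in numbers.** A reader might also blame session timing for the fact that 20 × 0.66 = 13.2 per arm falls below the minimum in "a minimum of 15 participants is required for an alpha of 0.05 and 95% power". That shortfall comes from multiplying 15 by 1.34 instead of dividing by 0.66 (15 / 0.66 = 22.7). It would arise under any questionnaire schedule and is a separate point.

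**The logs already capture adherence.** In part. They are not ignored: they are to confirm adherence, and all collected data are to be analysed. But no session count or group comparison is defined from them, and they cannot supply a missing questionnaire score.

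**People who leave may not answer reminders.** Some will not. Calendar timing mainly recovers those who skip or stop training but stay in contact, and the documents do not say how many that is. This is why non-response also has to be reported and tested.

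**Conclusion.** The point holds as a cheap improvement. It is certain from the text that the questionnaires are scheduled only by session number in the unsupervised weeks, that the meaning of that number is not stated, and that no follow-up of people who stop and no missing-score rule is given, although 34% dropout is expected. It is conditional that the existence of a score depends on adherence; this requires the sessions-done reading.

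The size is unknown. Under the assumed models a true 19.6 could appear as about 7 to 24, and as 19.6 exactly when loss and SDs are equal in both arms. That range illustrates and does not bound the bias. What a reader of the results would lack is any means of judging how far a score difference reflects the groups as allocated.

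**What to change.** 1. **Timing and follow-up.** Send PACES and EARS electronically at the end of weeks 2, 3 and 5 to every allocated participant, whatever their attendance, and record the number of sessions done by then. Ask for any outstanding final questionnaire at the planned week-6 visit. Smartphones and app access are already entry requirements, so delivery is feasible.
2. **Missing scores.** Report missing questionnaires by arm. Test the result over a pre-stated range of lower scores for those missing, varied separately in each arm and labelled as an assumption. For scale only: if 34% are missing in one arm and set δ points lower, that arm's mean moves by 0.34 × δ, so δ = 19.6 moves it by 6.7. That δ is the planned treatment effect, not evidence of how people who stop would score.
3. **Session count.** Alongside the scores, report and compare sessions logged out of 15 by arm for all 40 as allocated, counting a session with no log as not done.

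**Cost.** Wording changes, a few electronic reminders and one extra table; no added visits or participants. The planned primary score and sample size basis need not change. Making the session count primary is not proposed: the documents give no mean or SD for it.

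**Downsides.** Some scores will come from people no longer training, so they are not strictly after-session measures, and they will no longer coincide with the RPE sessions. Some reminders will go unanswered. The logs are self-recorded, so a missing log may not mean a missed session.

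### PACES and EARS are first given at session 6, after three unsupervised sessions, so early leavers have no questionnaire score; adding PACES at session 3 would reduce the resulting bias but might not remove it.

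*Combined protocol and SAP*

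**What the plan says.** All of this is in the Methods section of the combined protocol and SAP.

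- **Week 1 (sessions 1-3):** "The first week of the exercise intervention will consist of one-on-one supervised treadmill training, three times per week in the lab".
- **Weeks 2-5 (sessions 4-15):** "From week two to five, participants will follow the same exercise program on their own at their preferred gym three times per week". The stated purpose is "in order to examine free-living individuals adhere to two exercise programs".
- **Questionnaires:** the two statements of the schedule agree. PACES and EARS are completed "after the 6th, 9th and 15th session to assess their program adherence" and, in the later paragraph, "on the 6th, 9th and 15th session to assess their program adherence".
- **Perceived exertion:** same sessions, for example "at 10 and 20 minutes of exercise for MCEET group on the 6th, 9th and 15th session".
- **Heart rate:** logged by participants at every session, week 1 included. The logs and the questionnaires together are to confirm adherence.
- **Statistics paragraph:** programme adherence is the primary outcome. The analysis is two-way ANOVA with Tukey's test and a paired t-test. The sample is enlarged for "34% of drop out rate". No missing-data method is given, and no rule for participants who leave before session 6.

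**The concern.** Leaving early is likely to be related to what the questionnaires measure, because people who dislike their programme are the natural leavers. The plan's own hypothesis puts more of them in MCEET. If they go before session 6, the MCEET participants who remain score better than the whole arm would have done, and the difference between arms shrinks. Enlarging the sample replaces numbers but does nothing about who is missing, and no analysis can use a score that was never taken.

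The trial also moves participants from supervised to free-living exercise without an enjoyment score before the move. A lower score in one arm at session 6 could reflect the exercise itself or doing it alone.

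Session 3 is a lab visit that already takes place, just before the move, when few participants should have been lost.

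**Working it through.** **1. Timing.** 3 sessions per week x 5 weeks = 15 sessions. Sessions 6, 9 and 15 close weeks 2, 3 and 5. None falls in sessions 1-3, and sessions 4, 5 and 6 are unsupervised.

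**2. The plan's own figures.** The difference is 103.8 - 84.2 = 19.6. The root mean square of the two SDs is sqrt((9.4² + 19.1²)/2) = 15.05. At two-sided alpha 0.05 and 95% power this needs 16 (normal) or 17 (t) per arm, close to the stated 15. The stated 20 follows from 15 x 1.34 = 20.1. This point does not depend on the sample size.

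**3. How many have no score.** 34% of 20 is 6.8 leavers per arm. The documents do not say when they leave, so the unscored number lies between 0 and 6.8 per arm. At a constant rate (assumption), the per-session hazard is -ln(0.66)/15 = 0.0277.

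- Gone before session 6 (five sessions): 1 - exp(-5 x 0.0277) = 12.9%, about 2.6 per arm.
- Gone before session 3 (two sessions): 1 - exp(-2 x 0.0277) = 5.4%, about 1.1 per arm.

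**4. Effect on the estimated difference.** This was simulated with large samples, so that the results show bias rather than chance.

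- From the plan: HIIT mean 103.8, SD 9.4; MCEET mean 84.2, SD 19.1; 34% total drop-out.
- Assumed: means constant over sessions 3, 6, 9 and 15; equal within-person correlation of 0.5-0.7; drop-out odds 1.6-2.7 times higher per 15 points lower score; one third to two thirds of the drop-out hazard before session 6; nobody leaving before session 3. There were 12 combinations of these values.
- Estimators: the maximum-likelihood difference at session 15, with and without session 3, and the plain difference among completers.

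| Estimated difference (truth 19.6) | Drop-out depends on last recorded score | Drop-out depends on unrecorded current score |
|---|---|---|
| Model on sessions 6, 9, 15 | about 15.5-18.9 | about 14.0-17.6 |
| Same model plus session 3 | about 19.4-19.8 | about 15.4-18.6 |

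Under the first mechanism, completers alone give about 12.7-17.7. With no reading before session 6, 6-17% of HIIT participants (1.2-3.4 of 20) and 17-35% of MCEET participants (3.4-7.0 of 20) have no score.

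Session 3 moved the estimate towards the truth in all 12 combinations under each mechanism, by 0.6-4.3 points.

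**5. Why the first column looks so good.** There, drop-out depends only on a recorded score and everyone has a session-3 score. A likelihood model must then return about 19.6. If 20% of the drop-out hazard falls before session 3, the same mechanism gives 17.5-19.0 even with session 3.

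**The case against.** Several points against this are sound.

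- **Early leavers are not without data.** A reader might infer that they contribute nothing to the primary outcome, or that exercise is verified only in week 1. The documents do not support either reading: heart rate is logged at every session and helps confirm adherence, and stopping is itself non-adherence. Only direct supervision ends after week 1, and only the questionnaire scores are missing. The reference study behind the 19.6 concerns enjoyment by its title, so the simulation speaks for a questionnaire score and not for adherence as a whole.
- **Full attendance in week 1 is not given.** Nothing rules out withdrawal during sessions 1-3.
- **The reading needs a different analysis.** The plan has ANOVA and a paired t-test. A complete-case ANOVA with a session-3 column loses the same people. Part of the improvement over completers comes from the likelihood model alone.
- **EARS in week 1 would measure something else,** chiefly attendance at scheduled one-on-one visits.
- **The size is modest.** The standard error of the difference at 20 per arm is sqrt((9.4² + 19.1²)/20) = 4.8, larger than any of the gains in the working. The bias also runs against the trial's hypothesis, so this pattern of loss would not create a false positive.
- **Change from supervised to free-living exercise is not a stated objective,** so the missing starting point is a lost opportunity rather than a fault against the objectives.

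These points limit the claim but do not remove it. Heart-rate logs cannot replace a PACES score, and a shortfall of up to about 4 points (19.6 - 15.5 = 4.1) under the milder mechanism is systematic, so it would not shrink with more participants.

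**Conclusion.** The point stands in a limited form, as a cheap improvement. The first PACES and EARS scores come after three unsupervised sessions. Leavers before session 6 therefore have no questionnaire score, and no enjoyment score exists from the directly supervised week.

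If low scorers leave early, the difference in scores is understated. With a mixed model on the planned sessions the shortfall is about 0.7-4.1 points (19.6 less 18.9 and 15.5) when drop-out follows the last recorded score, and about 2.0-5.6 points (19.6 less 17.6 and 14.0) when it follows the unrecorded current score.

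It is tempting to conclude that a session-3 score corrects this. That holds only if drop-out follows recorded scores and nobody leaves before session 3, and the documents establish neither. Under the harsher mechanism a shortfall of about 1.0-4.2 points remains (19.6 less 18.6 and 15.4). The supported conclusion is that the reading reduces the bias.

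The direction rests on low scorers leaving early and more of them being in MCEET. The sizes rest on the assumed timing, strength and correlation, none of which is in the documents.

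**What to change.** - Add PACES at the end of the third supervised session, and keep sessions 6, 9 and 15 as planned.
- Analyse PACES with a pre-specified likelihood-based repeated-measures model that uses all available scores, in place of a complete-case ANOVA. The gain depends on this.
- Enter session 3 as the first outcome time point and not as a covariate, because it is taken after allocation.
- Do not pool a week-1 EARS score with later ones.
- Report, by arm, how many participants leave before session 3 and before session 6.

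The cost is a few minutes at an existing visit and one more exposure to the questionnaire, equal in both arms. It has to be decided before enrolment, because the score cannot be recovered later.
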